Median	XX.X	XX.X	XX.X	XX.X	XX.X	XX.X	XX.X
Maximum	XX	XX	XX	XX	XX	XX	XX
Cycle 1-Day 4							
n	XX	XX	XX	XX	XX	XX	XX
Mean	XX.X	XX.X	XX.X	XX.X	XX.X	XX.X	XX.X
SD	XX.XX	XX.XX	XX.XX	XX.XX	XX.XX	XX.XX	XX.XX
Minimum	XX	XX	XX	XX	XX	XX	XX
Median	XX.X	XX.X	XX.X	XX.X	XX.X	XX.X	XX.X
Maximum	XX	XX	XX	XX	XX	XX	XX
Change from Baseline to Cycle 1-Day 4							
n	XX	XX	XX	XX	XX	XX	XX
Mean	XX.X	XX.X	XX.X	XX.X	XX.X	XX.X	XX.X
SD	XX.XX	XX.XX	XX.XX	XX.XX	XX.XX	XX.XX	XX.XX
Minimum	XX	XX	XX	XX	XX	XX	XX
Median	XX.X	XX.X	XX.X	XX.X	XX.X	XX.X	XX.X
Maximum	XX	XX	XX	XX	XX	XX	XX

<repeat for Cycle 1 Day 10 visit>
<for Cycle 2 to last-1 Cycle, repeat for Day 1 visit and Day 4 visit>
<for the last Cycle, repeat for Day 22 visit and Day 28 follow-up visit>

[a] Baseline was the last value/result of assessment prior to or on day of first study treatment.

Program: (Program name.sas) (run on: DDMMYYYY HH:MM)

Filename: (Specify file name.rtf)

PROGRAMMING NOTES:

- Repeat for all hematology parameters: Hemoglobin, Hematocrit, Platelet count, RBC count, Reticulocytes, WBC Count with Differential, Neutrophils, Lymphocytes, Monocytes, Eosinophils, Basophils.

Protocol: CPX-POM-001

--- DELIVERY TYPE ----

Page 1 of X

Table 14.3-2.1.2 - Outside of Normal Range - Shift Table for Hematology Laboratory Parameters
 (Safety Population)

Dose group : CPX-POM 30 mg/m² (N=1)

Parameter/ Visit	Value at Visit	Baseline [a] value				Total
		Low n (%)	Normal n (%)	High n (%)	Low/High* n (%)	
Hemoglobin (unit)						
Cycle 1-Day 4 (N**=XX)	Low	XX (XXX.X)	XX (XXX.X)	XX (XXX.X)	XX (XXX.X)	XX (XXX.X)
	Normal	XX (XXX.X)	XX (XXX.X)	XX (XXX.X)	XX (XXX.X)	XX (XXX.X)
	High	XX (XXX.X)	XX (XXX.X)	XX (XXX.X)	XX (XXX.X)	XX (XXX.X)
	Low/High*	XX (XXX.X)	XX (XXX.X)	XX (XXX.X)	XX (XXX.X)	XX (XXX.X)
	Total	XX (XXX.X)	XX (XXX.X)	XX (XXX.X)	XX (XXX.X)	XX
Cycle 1-Day 10 (N**=XX)	Low	XX (XXX.X)	XX (XXX.X)	XX (XXX.X)	XX (XXX.X)	XX (XXX.X)
	Normal	XX (XXX.X)	XX (XXX.X)	XX (XXX.X)	XX (XXX.X)	XX (XXX.X)
	High	XX (XXX.X)	XX (XXX.X)	XX (XXX.X)	XX (XXX.X)	XX (XXX.X)
	Low/High*	XX (XXX.X)	XX (XXX.X)	XX (XXX.X)	XX (XXX.X)	XX (XXX.X)
	Total	XX (XXX.X)	XX (XXX.X)	XX (XXX.X)	XX (XXX.X)	XX

<for Cycle 2 to last-1 Cycle, repeat for Day 1 visit and Day 4 visit>
 <for the last Cycle, repeat for Day 22 visit and Day 28 follow-up visit>
 <repeat for all doses groups>

Percentage was based on the number of patients present at each visit with non-missing results for the considered parameter.

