Sponsor: CicloMed
Protocol: CPX-POM-001
Statistical Analysis Plan
(TFL shells):
Version 1.0 / 02FEB2018

Protocol: CPX-POM-001

--- DELIVERY TYPE ---

Page 1 of 1

Table 14.3-2.6 - Summary of Other Laboratory Data
(Safety Population)

Visit/ Parameter	CPX-POM 30 mg/m ² N=1	CPX-POM [D2] mg/m ² N=X	CPX-POM [D3] mg/m ² N=X	CPX-POM [D4] mg/m ² N=X	CPX-POM [D5] mg/m ² N=X	CPX-POM [D6] mg/m ² N=X	CPX-POM [D7] mg/m ² N=X
Screening visit							
HIV? [n (%)]							
No	XX (XX.X)	XX (XX.X)	XX (XX.X)	XX (XX.X)	XX (XX.X)	XX (XX.X)	XX (XX.X)
Yes	XX (XX.X)	XX (XX.X)	XX (XX.X)	XX (XX.X)	XX (XX.X)	XX (XX.X)	XX (XX.X)
Hepatitis A? [n (%)]							
No	XX (XX.X)	XX (XX.X)	XX (XX.X)	XX (XX.X)	XX (XX.X)	XX (XX.X)	XX (XX.X)
Yes	XX (XX.X)	XX (XX.X)	XX (XX.X)	XX (XX.X)	XX (XX.X)	XX (XX.X)	XX (XX.X)
Hepatitis B? [n (%)]							
No	XX (XX.X)	XX (XX.X)	XX (XX.X)	XX (XX.X)	XX (XX.X)	XX (XX.X)	XX (XX.X)
Yes	XX (XX.X)	XX (XX.X)	XX (XX.X)	XX (XX.X)	XX (XX.X)	XX (XX.X)	XX (XX.X)
Hepatitis C? [n (%)]							
No	XX (XX.X)	XX (XX.X)	XX (XX.X)	XX (XX.X)	XX (XX.X)	XX (XX.X)	XX (XX.X)
Yes	XX (XX.X)	XX (XX.X)	XX (XX.X)	XX (XX.X)	XX (XX.X)	XX (XX.X)	XX (XX.X)
Pregnancy test? [n (%)]							
No	XX (XX.X)	XX (XX.X)	XX (XX.X)	XX (XX.X)	XX (XX.X)	XX (XX.X)	XX (XX.X)
Yes	XX (XX.X)	XX (XX.X)	XX (XX.X)	XX (XX.X)	XX (XX.X)	XX (XX.X)	XX (XX.X)
Cycle 1-Day 1							
Pregnancy test? [n (%)]							
No	XX (XX.X)	XX (XX.X)	XX (XX.X)	XX (XX.X)	XX (XX.X)	XX (XX.X)	XX (XX.X)
Yes	XX (XX.X)	XX (XX.X)	XX (XX.X)	XX (XX.X)	XX (XX.X)	XX (XX.X)	XX (XX.X)

<for Pregnancy test, repeat for Day 1 visit of each cycle>

Program: (Program name.sas) (run on: DDMMYYYY HH:MM)

Filename: (Specify file name.rtf)

Sponsor: CicloMed
Protocol: CPX-POM-001
Statistical Analysis Plan
(TFL shells):
Version 1.0 / 02FEB2018

Table 14.3-3.1 - Summary of Vital Signs
(Safety Population)

Replicate of Table 14.3-2.1.1

PROGRAMMING NOTES:

- Update "laboratory parameter" by "parameter"
- Vital signs include pulse rate, blood pressure, respiratory rate, oxygen saturation and temperature
- On Days 1 and 5, vital signs are measured at pre-dose and at 6-hour intervals post-dose.

Table 14.3-3.2 - Summary of Abnormal Vital Signs
(Safety Population)

Parameter/ Visit/ Category	CPX-POM 30 mg/m ² N=1	CPX-POM [D2] mg/m ² N=X	CPX-POM [D3] mg/m ² N=X	CPX-POM [D4] mg/m ² N=X	CPX-POM [D5] mg/m ² N=X	CPX-POM [D6] mg/m ² N=X	CPX-POM [D7] mg/m ² N=X
Pulse rate (bpm)							
Cycle 1							
Baseline [a]*	XX	XX	XX	XX	XX	XX	XX

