> 150 bpm	XX (XXX.X)	XX (XXX.X)	XX (XXX.X)	XX (XXX.X)	XX (XXX.X)	XX (XXX.X)	XX (XXX.X)
[101-150] bpm	XX (XXX.X)	XX (XXX.X)	XX (XXX.X)	XX (XXX.X)	XX (XXX.X)	XX (XXX.X)	XX (XXX.X)
< 55 bpm	XX (XXX.X)	XX (XXX.X)	XX (XXX.X)	XX (XXX.X)	XX (XXX.X)	XX (XXX.X)	XX (XXX.X)
Cycle 1-Day 2 *							
> 150 bpm	XX (XXX.X)	XX (XXX.X)	XX (XXX.X)	XX (XXX.X)	XX (XXX.X)	XX (XXX.X)	XX (XXX.X)
[101-150] bpm	XX (XXX.X)	XX (XXX.X)	XX (XXX.X)	XX (XXX.X)	XX (XXX.X)	XX (XXX.X)	XX (XXX.X)
< 55 bpm	XX (XXX.X)	XX (XXX.X)	XX (XXX.X)	XX (XXX.X)	XX (XXX.X)	XX (XXX.X)	XX (XXX.X)

<repeat for next Cycle 1 visits>
<for Cycle 2 to last-1 Cycle, repeat for Day 1 visit to Day 6 visit>
<for the last Cycle, repeat for Day 1 visit to Day 6 visit, Day 22 visit and Day 28 follow-up visit>

* Denominator for the percentages.
[a] Baseline was the last value/result of assessment prior to or on day of first study treatment.
> 150 bpm: Very High values
[101-150] bpm: High values
< 55 bpm: Low values

Sponsor: CicloMed
Protocol: CPX-POM-001
Statistical Analysis Plan
(TFL shells):
Version 1.0 / 02FEB2018

Protocol: CPX-POM-001

--- DELIVERY TYPE ---

Page 2 of 3

Table 14.3-3.2 - Summary of Abnormal Vital Signs
(Safety Population)

Parameter/ Visit/ Category	CPX-POM 30 mg/m ² N=1	CPX-POM [D2] mg/m ² N=X	CPX-POM [D3] mg/m ² N=X	CPX-POM [D4] mg/m ² N=X	CPX-POM [D5] mg/m ² N=X	CPX-POM [D6] mg/m ² N=X	CPX-POM [D7] mg/m ² N=X
Systolic Blood Pressure (mmHg)							
Baseline [a]*	XX	XX	XX	XX	XX	XX	XX
>= 161 mmHg	XX (XXX.X)	XX (XXX.X)	XX (XXX.X)	XX (XXX.X)	XX (XXX.X)	XX (XXX.X)	XX (XXX.X)
[131-160] bpm	XX (XXX.X)	XX (XXX.X)	XX (XXX.X)	XX (XXX.X)	XX (XXX.X)	XX (XXX.X)	XX (XXX.X)
< 95 mmHg	XX (XXX.X)	XX (XXX.X)	XX (XXX.X)	XX (XXX.X)	XX (XXX.X)	XX (XXX.X)	XX (XXX.X)
Cycle 1-Day 2 *	XX	XX	XX	XX	XX	XX	XX
>= 161 mmHg	XX (XXX.X)	XX (XXX.X)	XX (XXX.X)	XX (XXX.X)	XX (XXX.X)	XX (XXX.X)	XX (XXX.X)
[131-160] bpm	XX (XXX.X)	XX (XXX.X)	XX (XXX.X)	XX (XXX.X)	XX (XXX.X)	XX (XXX.X)	XX (XXX.X)
< 95 mmHg	XX (XXX.X)	XX (XXX.X)	XX (XXX.X)	XX (XXX.X)	XX (XXX.X)	XX (XXX.X)	XX (XXX.X)

<repeat for next Cycle 1 visits>

<for Cycle 2 to last-1 Cycle, repeat for Day 1 visit to Day 6 visit>

<for the last Cycle, repeat for Day 1 visit to Day 6 visit, Day 22 visit and Day 28 follow-up visit>

* Denominator for the percentages.

[a] Baseline was the last value/result of assessment prior to or on day of first study treatment.

>= 161 bpm: Very High values

[131-160] bpm: High values

< 95 bpm: Low values

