Protocol: CPX-POM-001
Statistical Analysis Plan
(TFL shells):
Version 1.0 / 02FEB2018

Protocol: CPX-POM-001

--- DELIVERY TYPE ---

Page 1 of X

Listing 16.1.7-1 - Treatment Administration
 (All Patients)

Center/ Patient	Visit	CPX-POM Dose group	CPX-POM Dose Amount per Prot.?	If no, Reason for Adjustment?	Total Inf. Bag vol. of Sal. and CPX-POM (ml)	Was Total Vol. Inf.?	If no, actual Vol. Inf.?	Adm. Date (Day) Inf. Start Time- Inf. End Time	Arm Used for IV	Infusion Interrupted?
XXXXXXXX	BAS	30 mg/m ²	Yes		XXX	Yes		DDMMYYYY (XX) HH:MM-HH:MM	Right	
	C1 TRT D2	30 mg/m ²	Yes		Yes	Yes		DDMMYYYY (XX) HH:MM-HH:MM	Right	
	C1 TRT D3	30 mg/m ²	Yes		XXX	Yes		DDMMYYYY (XX) HH:MM-HH:MM	Right	
	C1 TRT D4	30 mg/m ²	Yes		XXX	Yes		DDMMYYYY (XX) HH:MM-HH:MM	Right	
	C1 TRT D5	30 mg/m ²	No	Adverse event	XXX	No	XXX	DDMMYYYY (XX) HH:MM-HH:MM	Right	Yes [a]

<repeat for Days 1,2,3,4 and 5 of next cycles if relevant>

Prot.: Protocol; Inf.: Infusion/Infused; Vol.: Volume; Sal.: Saline; Adm.: Administration; Inter.: Interruption/Interrupted;
 IV: Intravenous

[a]: see further details regarding the infusion interruption in Listing 16.1.7-2

Program: (Program name.sas) (run on: DDMMYYYY HH:MM)

Filename: (Specify file name.rtf)

PROGRAMMING NOTES:

- Listing to be sorted by increasing CPX-POM dose.

Sponsor: CicloMed
Protocol: CPX-POM-001
Statistical Analysis Plan
(TFL shells):
Version 1.0 / 02FEB2018

Protocol: CPX-POM-001

--- DELIVERY TYPE ---

Page 1 of X

Listing 16.1.7-2 - Infusion Interruption
 (All Patients)

Center/ Patient	Visit	CPX-POM Dose group	Reason for Inf. Inter.?	Specify	Adm. Date (Day) Time Inf. Inter.	Inf. Rest.?	Time Inf. Restarted	Reason for Not Restarting?	Specify	Inf. Site React.?
XXXXXXXX	C1 TRT D5	30 mg/m ²	Infusion reaction	XXXXX	DDMMYYYY (XX) HH:MM	No		Infusion reaction	XXXXX	Yes
XXXXXXXX	C2 TRT D2	[D2] mg/m ²	Technical problem	XXXXX	DDMMYYYY (XX) HH:MM	Yes	HH:MM		XXXXX	No

<cont>

Inf.: Infusion; Inter.: Interrupted; Rest.: Restarted; React.: Reaction.

Program: (Program name.sas) (run on: DDMMYYYY HH:MM)

Filename: (Specify file name.rtf)

PROGRAMMING NOTES:

- Listing to be sorted by increasing CPX-POM dose.

Listing 16.2.1-1.1 - Preface to Inclusion and Exclusion Criteria

Protocol Version	Inclusion/Exclusion No.	Inclusion / Exclusion Text

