- Repeat for the other CPX-POM doses by increasing order.
- Select all AEs where SAE = Yes.
- Remove column 'SAE' and remove SAE from footnote.

Listing 16.2.7-3 - Adverse Events Leading to Discontinuation
(All Patients)

Replicate of Listing 16.2.7-1

PROGRAMMING NOTES:

- Repeat for the other CPX-POM doses by increasing order.
- Select all AEs where action taken = permanently discontinued.

Listing 16.2.7-4 - Adverse Events Leading to Death
(All Patients)

Replicate of Listing 16.2.7-1

PROGRAMMING NOTES:

- Repeat for the other CPX-POM doses by increasing order.
- Select all AEs where outcome = Fatal

Sponsor: CicloMed
Protocol: CPX-POM-001
Statistical Analysis Plan
(TFL shells):
Version 1.0 / 02FEB2018

Protocol: CPX-POM-001

--- DELIVERY TYPE ----

Page 1 of X

Listing 16.2.8-1 - Patients Laboratory Profile: Hematology
 (All Patients)

CPX-POM Dose Group: 30 mg/m²

Center/ Patient	Visit	Assessment		Study Day	Parameter (Unit)	Normal Range	Result	CTCAE grade	Change from Baseline	Clinical Interpretation
		Date	Time							
XXXX	BAS	DDMMYYYY	HH:MM	XXX	XXXXXXXX (XXXX)	XXXXXX	XX	Grade 1		Normal
	C1 TRT D1	DDMMYYYY	HH:MM	XXX	XXXXXXXX (XXXX)	XXXXXX	XX L/H	Grade 2	XXXX	Abnormal, NCS
	C1 TRT D4	DDMMYYYY	HH:MM	XXX	XXXXXXXX (XXXX)	XXXXXX	XX L/H	Grade 2	XXXX	Abnormal, NCS
	C1 TRT D10	DDMMYYYY	HH:MM	XXX	XXXXXXXX (XXXX)	XXXXXX	XX L/H	Grade 3	XXXX	Abnormal, CS

<for Cycle 2 to last-1 cycle, repeat for Day 1 visit and Day 4 visit if relevant>
<for the last cycle, repeat also for Day 22 visit and Day 28 visit>

Study Day was from the date of first dose of CPX-POM administration. Dates are displayed as DDMMYYYY, -- represents an unknown date component. Baseline was the last non-missing assessment prior or on the first dose date. SI units and results presented. L/H = low/high value based upon normal ranges. R = repeat/unscheduled assessments. CS = Clinically Significant; NCS = Not Clinically Significant; ND = Not Done.

Program: (Program name.sas) (run on: DDMMYYYY HH:MM)

Filename: (Specify file name.rtf)

PROGRAMMING NOTES:

- Repeat for the other CPX-POM doses by increasing order.

Sponsor: CicloMed
Protocol: CPX-POM-001
Statistical Analysis Plan
(TFL shells):
Version 1.0 / 02FEB2018

Listing 16.2.8-2 - Patients Laboratory Profile: Clinical Chemistry
(All Patients)

Replicate of Listing 16.2.8-1

PROGRAMMING NOTES:

- Listing to be sorted by increasing order.

Listing 16.2.8-3 - Patients Laboratory Profile: Coagulation and Thyroid Panel
(All Patients)

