Replicate of Listing 16.2.8-1

PROGRAMMING NOTES:

- Listing to be sorted by increasing order.
- Only Day 1 of each cycle.

Listing 16.2.8-4 - Patients Laboratory Profile: Urinalysis
(All Patients)

Replicate of Listing 16.2.8-1

PROGRAMMING NOTES:

- Listing to be sorted by increasing order.
- Replace 'Day 4' by 'Day 5' for each cycle.

Sponsor: CicloMed
Protocol: CPX-POM-001
Statistical Analysis Plan
(TFL shells):
Version 1.0 / 02FEB2018

Protocol: CPX-POM-001

--- DELIVERY TYPE ---

Page 1 of X

Listing 16.2.8-5 - Vital Signs
 (All Patients)

CPX-POM Dose Group: 30 mg/m²

Center/ Patient	Visit	Assessment		Study Day	Parameter (unit)	Position	Result	Change from Baseline
		Date	Time					
XXXX	BAS	DDMMYYYY	HH:MM	XXX	Pulse Rate (bpm)	Supine	XXX +	
					Respiratory Rate (bpm)	Supine	XXX	
					Systolic BP (mmHg)	Supine	XXX	
					Diastolic BP (mmHg)	Supine	XXX	
					Oxygen Saturation (mmHg)		XXX	
					Body Weight (kg)		XXX.X	
					Temperature (C)		XX.X	
	C1 TRT D2	DDMMYYYY	HH:MM	XXX	Pulse Rate (bpm)	Supine	XXX +	XX
					Respiratory Rate (bpm)	Supine	XXX	XX
					Systolic BP (mmHg)	Supine	XXX	XX
					Diastolic BP (mmHg)	Supine	XXX	XX
					Oxygen Saturation (mmHg)		XXX	XX
					Body Weight (kg)		XXX.X	X.X
					Temperature (C)		XX.X	X.X

<repeat for Day 3, Day 4, Day 5, Day 6 and Day 10 visits of Cycle 1>
 <for Cycle 2 to last-1 cycle, repeat from Day 1 to Day 6 visits if relevant>
 <for the last cycle, repeat also for Day 22 visit and Day 28 follow-up visit>

Study Day was from the date of first dose of CPX-POM administration. Dates are displayed as DDMMYYYY. Baseline was the last non-missing assessment prior or on the first dose.

+ Results of clinical importance (see SAP). BP = Blood Pressure; bpm = beats per minute; ND = Not Done.

Program: (Program name.sas) (run on: DDMMYYYY HH:MM)

Filename: (Specify file name.rtf)

PROGRAMMING NOTES:

- Repeat for all doses groups

Sponsor: CicloMed
Protocol: CPX-POM-001
Statistical Analysis Plan
(TFL shells):
Version 1.0 / 02FEB2018

Protocol: CPX-POM-001

--- DELIVERY TYPE ----

Page 1 of X

Listing 16.2.8-6 - ECG Results and Interpretation
 (All Patients)

CPX-POM Dose Group: 30 mg/m²

Center/ Patient	Visit	Assessment Date (Day)	Parameter (unit)	Clinician Interpretation	Result	Change from baseline
XXXX	BAS	DDMMYYYY (XXX)	Heart Rate (bpm)	Normal	XXX	
			PR interval (msec)	Normal		
			QRS duration (msec)	Normal		
			QT interval (msec)	Normal		
			QTcB interval (msec)	Normal		
			QTcF interval (msec)	Normal		

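### Read literally, the vital-sign baseline footnote in the supplied SAP shells selects a post-dose Day 1 reading whenever the first infusion starts before about 17:50

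*SAP*

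**What the plan says.** - **Baseline rule in the tables.** Footnote [a] of SAP Table 14.3-3.2 (abnormal vital signs) states "Baseline was the last value/result of assessment prior to or on day of first study treatment". Table 14.3-3.1 (vital-sign summary) is specified as a replicate of Table 14.3-2.1.1, which carries the same footnote and rows such as "Change from Baseline to Cycle 1-Day 4". The programming notes to Table 14.3-3.1 leave the footnote unchanged.
- **Schedule.** Those notes add: "On Days 1 and 5, vital signs are measured at pre-dose and at 6-hour intervals post-dose". Protocol Table 1, footnote 16, gives the same schedule. Footnote 1 keeps patients in the unit for at least 12 hours on Days 1 and 5 of Cycle 1.
- **Rows.** Table 14.3-3.2 goes from Baseline to Cycle 1-Day 2 and then says "<repeat for next Cycle 1 visits>". No separate row is given for Day 1 after dosing.
- **Listing.** Listing 16.2.8-5 (vital signs) says "Baseline was the last non-missing assessment prior or on the first dose". The hematology and ECG listings (16.2.8-1 and 16.2.8-6) say "Baseline was the last non-missing assessment prior or on the first dose date".

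**The concern.** A baseline should be free of study drug. The footnote limits baseline by calendar day and takes the last value on that day, with no requirement that it precede the infusion. For an assessment made once on Day 1 before dosing, this is harmless. Vital signs are also scheduled after dosing on the same day, so the last value of the day is usually a treated one.

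The two tables are affected differently. Table 14.3-3.1 reports changes, so an early effect that persists to the baseline reading is removed from every later change. Table 14.3-3.2 uses absolute cut-offs, so a patient who is abnormal only after the first infusion appears under Baseline, as if the abnormality had been present beforehand. In a first-in-human study with dose groups of one to six patients, these tables are a main summary of vital signs by dose.

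**Working it through.** **Inputs**

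- Infusion length: 10 minutes (protocol section 6.1.4).
- Readings on Day 1: before dosing and 6-hourly afterwards (protocol Table 1, footnote 16). The documents do not say when the 6-hourly readings end. The 12-hour minimum stay covers a 6 h reading and makes a 12 h reading possible.
- Dose-group sizes: 1 in accelerated titration, 3 to 6 in standard cohorts (protocol Table 2).

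**Step 1: which reading the footnote selects.** Let T be the clock time at which the first infusion starts, and count hours from the end of infusion.

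- The 6 h reading falls on the dosing day if T + 0:10 + 6:00 < 24:00, so T < 17:50.
- The 12 h reading falls on the dosing day if T + 0:10 + 12:00 < 24:00, so T < 11:50.
- Counted from the start of infusion, the limits are 18:00 and 12:00.

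| First infusion starts | Readings run to 12 h | Only a 6 h reading |
|---|---|---|
| Before 11:50 | 12 h post-dose | 6 h post-dose |
| 11:50 to before 17:50 | 6 h post-dose | 6 h post-dose |
| 17:50 or later | Pre-dose | Pre-dose |

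Stepping through start times from 07:00 to 19:00, with readings at 6 h and 12 h, agrees: the 12 h reading for the tested starts from 07:00 to 11:45, the 6 h reading from 12:00 to 17:45, and the pre-dose reading at 18:00 and 19:00. With baseline restricted to readings before the infusion starts, the pre-dose value is selected at every start time tested.

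**Step 2: Table 14.3-3.1.** Let P be the pre-dose reading, V a later reading, and r the part of the drug effect still present at the reading used as baseline. Leaving other variation aside, the baseline used is P + r, so the change shown is V − (P + r) = (V − P) − r. The documents give no time course for vital signs, so r cannot be given a value. If r = 0, the change is undistorted.

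**Step 3: Table 14.3-3.2.** If every patient in the group has a baseline reading, one patient who is abnormal only after dosing on Day 1 moves the Baseline row by 1/1 = 100, 1/3 = 33.3 or 1/6 = 16.7 percentage points. Correcting the footnote alone would take the reading out of Baseline but leave no separate row to hold it.

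**Step 4: other uses of the footnote.** The scheduled 12-lead ECG on Cycle 1 Day 1 precedes drug administration (protocol Table 1, footnote 17), and no post-dose laboratory draw is scheduled that day. The wording does no harm for those scheduled assessments.

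**The case against.** The best reply is that nobody intends a post-dose baseline and that the SAP body probably says so. The supplied document is labelled as table, figure and listing shells, Listing 16.2.8-5 refers the reader to the SAP, and protocol section 9 leaves the finalized analysis plans to the SAP. Table 14.3-3.1 must be adapted from its laboratory parent in any case, since vital signs are taken on more days than that shell shows, and the note on 6-hourly readings may prompt a programmer to separate them. All outputs concerned are descriptive. These points limit the finding to the supplied shells and to a wording defect. They do not remove it: the shells are what is programmed from, the rule they state gives the wrong value, and nothing supplied overrides it.

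Some stronger readings are tempting but not supported:

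- *The tables and the listing use conflicting baselines.* A reader might infer this because Listing 16.2.8-5 ties baseline to the dose rather than its date. The same sentence in the other listings ends with the word for date, so a dropped word is the likelier explanation. The wording needs only to be made consistent.
- *Listing 16.2.8-5 cannot show Day 1 post-dose readings.* Its rows go from BAS to Day 2 and then "<repeat for Day 3, Day 4, Day 5, Day 6 and Day 10 visits of Cycle 1>". But Listing 16.1.7-1 places the first infusion under BAS, Listing 16.2.3-2 uses BAS for the Day 1 pregnancy test, and protocol section 6.2 equates baseline with Study Visit 2, which is Day 1. Timed post-dose readings could sit under BAS, although Listing 16.2.8-1 does show BAS and Day 1 separately.
- *The bias can be stated in mmHg.* It cannot, because the documents give no vital-sign effect or time course.
- *The baseline defect extends to Holter output.* The absence of a Holter shell is a separate matter of a missing output and depends on SAP text that was not supplied.

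**Conclusion.** The point holds for the supplied shells. As worded, the baseline for Tables 14.3-3.1 and 14.3-3.2 is a post-dose reading for any first infusion starting before about 17:50, which covers ordinary daytime dosing. This rests on the scheduled 6 h reading being taken and on the footnote being applied literally. It does not show that any analysis will be run that way.

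For Table 14.3-3.2, each affected patient shifts the Baseline row by 16.7 to 100 percentage points, depending on group size; how many patients would be affected is unknown. For Table 14.3-3.1, the bias equals whatever drug effect remains at the baseline reading, which may be nil.

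The MTD rule counts DLTs, and TEAE tables use onset relative to first dose, so neither depends on this footnote. The defect is modest in consequence but cheap to remove, and worth correcting before programming.

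**What to change.** 1. In Tables 14.3-3.1 and 14.3-3.2 and in Listing 16.2.8-5, define baseline as the last non-missing assessment before the start of the first CPX-POM infusion. Use identical wording in all three and align it with any definition in the SAP body.
2. In Tables 14.3-3.1 and 14.3-3.2, show the Day 1 and Day 5 vital signs as separate labelled pre-dose and post-dose time points. Without this, correcting the footnote would leave the Day 1 post-dose readings with no row of their own in Table 14.3-3.2.

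The cost is a footnote edit and a few descriptive rows. The data needed are already in the listing shells: Listing 16.1.7-1 has "Inf. Start Time- Inf. End Time", and Listing 16.2.8-5 has the date and time of each vital-sign assessment.
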